6.2.3.3 Extended follow-up period

6.2.3.3.1 Follow-up for progression

For patients who did not progress, additional follow-up visits after the EoR visit will be performed every 6 weeks plus/minus 3 days.

The follow-up for progression period will end at the earliest of the following events:

- Lost to follow-up
- Disease progression
- Start of a new anti-cancer therapy
- Death
- End of whole trial as specified in [Section 8.6](#)

At the end of the follow-up period, the EoFU (End of Follow-Up) visit has to be performed. The following will be obtained and / or performed during the follow-up visits and the EoFU visit.

- Record all related SAEs and all related AESI and a follow-up of adverse events ongoing since End of REP to EoFU as entered in source data
- Concomitant medications for treatment of an adverse event reported in the (e)CRF including trade name, indication and dates of administration
- Perform tumour assessment and imaging
- Treatment and date with any other anti-cancer drug including the name and type of the anti-cancer drug and/or best supportive care
- Outcome (date of and reason for death, in case the patient had PD the actual date of PD shall be recorded)
- Samples for PK, [REDACTED] at first Follow-up (FU1)

6.2.3.3.2 Follow-up for Overall Survival

Not applicable.

6.2.3.4 Trial completion for an individual patient

A patient is considered to have completed the trial in case any of the following applies:

- Completion of planned follow-up period
- Lost to follow-up
- Withdrawal to be followed-up
- Death

At the earliest of the above criteria, the Patient Completion (PC) information should be entered in the CRF.

6.2.3.5 Trial completion

The end of the trial will occur when the last patient completes his/her REP. In case patients would be still on treatment when data base is locked and the Clinical Trial Report (CTR) is being drafted, these patients will be maintained in the trial and may continue treatment as long as they have clinical benefit (no PD, no drug-related adverse events requiring discontinuation, no new anti-cancer treatment started) and patient is willing to continue. For these patients, no blood sample will be collected for PK [REDACTED] analysis. After the discontinuation of these patients, the data collected after the database lock (DBL) will be provided as separate listings and will not lead to any further updating of tables produced for section 15 of the CTR unless deemed necessary. These listings will be included in a revised CTR.

7. STATISTICAL METHODS AND DETERMINATION OF SAMPLE SIZE

7.1 STATISTICAL DESIGN – MODEL

This is phase I, open-label, dose-escalating trial to determine the MTD and RP2D for BI 836880 in patients with solid tumor. The MTD may be considered reached if the probability that the true DLT rate is in target interval (16% - 33%) is sufficiently large. Dose escalation and determination of MTD will be guided by a Bayesian 2-parameter logistic regression model with overdose control ([R13-4803](#); [R13-4806](#)). These designs have been shown to be superior regarding the precision of MTD determination compared to 3+3 designs and have been particularly endorsed by the FDA ([R13-4881](#)).

The model is formulated as follows:

$$\text{logit}(p(d)) = \log(\alpha) + \beta * \log(d/d^*),$$

where $\text{logit}(p) = \log(p/(1-p))$.

$p(d)$ represents the probability of having a DLT in the first cycle at dose d , $d^* = 720\text{mg}$ is the reference dose, allowing for the interpretation of α as the odds of a DLT at dose d^* , and $\theta = (\log(\alpha), \log(\beta))$ with $\alpha, \beta > 0$ is the parameter vector of the model.

Since a Bayesian approach is applied, a prior distribution $\pi(\theta)$ for the unknown parameter vector θ needs to be specified. This prior distribution will be specified as a mixture of three multivariate normal distributions, i.e.

$$\pi(\theta) = \varphi_1 \pi_1(\theta) + \varphi_2 \pi_2(\theta) + \varphi_3 \pi_3(\theta)$$

with

$\varphi_i, i = 1, 2, 3$ the prior mixture weights ($\varphi_1 + \varphi_2 + \varphi_3 = 1$)

and

$$\pi_i(\theta) = \text{MVN}(\mu_i, \Sigma_i)$$

the multivariate normal distribution of the i -th component with mean vector μ_i and covariance matrix Σ_i , with

$$\Sigma_i = \begin{pmatrix} \sigma_{i,11}^2 & \sigma_{i,11}\sigma_{i,22}\rho_i \\ \sigma_{i,11}\sigma_{i,22}\rho_i & \sigma_{i,22}^2 \end{pmatrix}$$

Mixture prior distributions have the advantage that they allow for specification of different logistic dose-toxicity curves, therefore making the prior more robust.

Prior derivation

For the current study, no relevant information in the form of human data was available, since no study in a comparable population has been conducted. Therefore, the three mixture components were established as follows:

1. A weakly informative prior was derived to reflect a priori assumption that the median DLT rate at the starting dose of 40mg would equal 0.1%, and the median DLT rate at the anticipated MTD of 720mg would equal 20%. This yields $\mu_1 = (-0.333, 0.647)$. The standard deviations were set such that large uncertainty about the parameter means is reflected, and the correlation was set to 0, thus yielding $\sigma_{1,11} = 2$, $\sigma_{1,22} = 1$ and $\rho_1 = 0$, respectively. The prior weight φ_1 for the first component was chosen as 0.9.
2. A high-toxicity weakly informative prior was derived to reflect the case that the compound would be much more toxic than expected. For this prior component, it was assumed that the median DLT rate at the starting dose of 40mg would equal 10%, and the median DLT at the anticipated MTD of 720mg would equal 50%. These assumptions yield $\mu_2 = (0.419, -0.274)$. The standard deviations and correlations were set identical to the weakly informative prior, i.e. $\sigma_{2,11} = 2$, $\sigma_{2,22} = 1$ and $\rho_2 = 0$, respectively. The prior weight φ_2 for the second component was chosen as 0.05.
3. A low-toxicity weakly informative prior was derived to reflect the case that the compound would be much less toxic than expected. For this prior component, it was assumed that the median DLT rate at the starting dose of 40mg would equal 0.1%, and the median DLT at the anticipated MTD of 720mg would equal 2%. These assumptions yield $\mu_3 = (-3.316, 0.042)$, i.e. basically a flat curve. The standard deviations and correlations were set to $\sigma_{3,11} = 5$, $\sigma_{3,22} = 0.01$, therefore almost fixing the slope parameter to its mean. The correlation was set to 0, i.e. $\rho_3 = 0$. The prior weight φ_3 for the third component was chosen as 0.05.

A summary of the prior distribution is provided in [Table 7.1:1](#). Additionally, the prior probabilities of DLT at different doses, as well as the corresponding probability of under-, targeted and overdosing, are shown in [Table 7.1:2](#). Graphically, the prior medians with accompanying 95% credible intervals are shown in [Figure 7.1:1](#). As can be seen from both, the Table and the Figure, the prior medians of the DLT probabilities are in-line with the prior medians derived from the weakly informative prior, and the uncertainty around the medians is large, showing the low amount of information this prior provides. This is also supported by the prior sample size, i.e. the information contained in the prior. This is approximately equal to 1.2 patients, i.e. less than or around half of the weight the first cohort in the study will have.

Table 7.1: 1 Summary of prior distribution

Prior Component	Mixture Weight	Mean vector	SD vector	Correlation
1: Weakly inf.	0.900	-0.333 0.647	2.000, 1.000	0.000
2: High Tox	0.050	0.419 -0.274	2.000, 1.000	0.000
3: Low Tox	0.050	-3.316 0.042	5.000, 0.010	0.000

Table 7.1: 2 Prior probabilities of DLT at selected doses

Dose	Probability of true DLT rate in			Mean	SD	Quantiles		
	[0–0.16)	[0.16–0.33)	[0.33–1]			2.5%	50%	97.5%
40	0.877	0.049	0.074	0.069	0.172	<.001	0.001	0.703
120	0.813	0.071	0.116	0.104	0.208	<.001	0.006	0.812
360	0.685	0.110	0.205	0.176	0.258	<.001	0.043	0.899
720	0.515	0.153	0.332	0.274	0.295	<.001	0.148	0.944
1250	0.269	0.164	0.566	0.444	0.318	0.005	0.410	0.975

Doses printed in bold face meet the overdose criterion ($P(\text{overdose}) < 0.25$)

[figure not shown]

Figure 7.1: 1 Prior medians and 95% credible intervals

The MTD may be considered reached if the following criteria is fulfilled

1. At least 1 DLT on the trial and either
2. At least 6 patients haven been treated at the MTD and the posterior probability of the true DLT rate in the target interval (16%-33%) is above 50%, OR
3. At least 18 patients in the trial with 6 patients have been treated at MTD.

Statistical model assessment

The model was assessed using two different metrics:

1. Hypothetical data scenarios: for various potential data constellations as they could occur in the actual trial, the maximal next doses as allowed by the model and by the 100% escalation limit are investigated. Data scenarios thus provide a way to assess the “on-study” behaviour of the model.
2. Simulated operating characteristics: these illustrate for different assumed true dose-toxicity relationships, how often a correct dose would be declared as MTD by the model. They are a way to assess the “long-run” behaviour of the model.

In summary, the model showed very good behaviour as assessed by these metrics. More details can be found in [Appendix 10.6](#).

Based upon these design considerations, the trial will be analysed using general linear models which will include terms for centre and disease severity as covariates.

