10.6 STATISTICAL APPENDIX INCLUDING MODEL PERFORMANCE AND DATA SCENARIOS

The model was assessed by two different metrics: hypothetical on-study data scenarios and long-run operating characteristics.

Hypothetical data scenarios

Hypothetical data scenarios are shown in [Table 10.6: 1](#). These scenarios reflect potential on-study data constellations and related escalation as allowed by the model and the 200% escalation limit or doses of interest. For each scenario, the probability of overdose for the current dose, as well as the next potential dose and related probabilities of under-dosing, target dose and over-dosing are shown. A new cohort will be open for enrolment after the review on data from the previous cohort is completed by DSB.

For example, scenario 1 represents the case that no DLT is observed in two patients at the starting dose of 40mg. In this case, the next dose permitted by the model and by the 200% escalation rule is 120mg. Scenario 4 represents the case that no DLTs are observed in the first cohort of two patients at 40mg, and 1 DLT is observed in the second cohort of three patients at 120mg. In this case, the model requires to re-enroll at the current dose level of 120mg. Scenario 5 shows the case that 2 DLTs are observed in the second cohort of three patients at 120mg. The model then allows a de-escalation.

Finally, scenario 6 and 7 illustrate the case where no DLTs are seen in the first three cohorts. In scenario 6, no DLT is observed at 720mg, either. However, the model does not allow the escalation to 1250mg for safety concerns despite the fact that no DLTs are observed in the first four cohorts. On the other hand, scenario 7 presents the case that 1 DLT is seen at 720mg. In this case, no escalation to 1250mg is allowed as well. These two cases illustrate the adaptive behaviour of the model even in extreme situations.

Table 10.6: 1 Hypothetical data scenarios.

Scenario	Cohort	Dose (mg)	# DLT	# Pat	Current Dose: P(OD)	Next Dose	Next Dose		
							P(UD)	P(TD)	P(OD)
1	1	40	0	2	0.013	120	0.894	0.062	0.044
2	1	40	1	3	0.278	N/A	N/A	N/A	N/A
3	1	40	0	2					
	2	120	0	2	0.013	360	0.816	0.103	0.081
4	1	40	0	2					
	2	120	1	3	0.194	120	0.497	0.309	0.194
5	1	40	0	2					
	2	120	2	3	0.575	40	0.434	0.330	0.236
6	1	40	0	2					
	2	120	0	2					
	3	360	0	3					
	4	720	0	3	0.025	720	0.878	0.097	0.025
7	1	40	0	2					
	2	120	0	2					
	3	360	0	3					
	4	720	1	3	0.224	720	0.436	0.340	0.224

Operating characteristics

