Operating characteristics are a way to assess the long-run behaviour of a model. Under an assumed true dose-toxicity curve, metrics such as the probability of recommending a dose with true DLT rate in the target interval can be approximated via simulation. [Table 10.6: 2](#) describes 5 assumed true dose-toxicity scenarios which were used to assess the operating characteristics of the model. These scenarios reflect a wide range of possible cases as follows:

- Scenario 1: aligned with prior medians
- Scenario 2: high-toxicity scenario
- Scenario 3: low-toxicity scenario
- Scenario 4: low-tox followed by high-tox
- Scenario 5: non-logistic dose-toxicity scenario

Table 10.6: 2

Assumed true dose-toxicity scenarios

Scenario		Dose (mg)				
		40	120	360	720	1250
1 (Prior)	P(DLT)	0.069	0.104	0.176	0.274	0.444
2 (High Tox)		0.100	0.204	0.371	0.500	0.603
3 (Low Tox)		0.001	0.006	0.039	0.180	0.250
4 (Non-Logistic)		0.040	0.180	0.280	0.360	0.380
5 (Low-High)		0.001	0.010	0.180	0.317	0.600

For each of these scenarios, 1000 trials were simulated. It was then assessed how often a dose was declared as MTD with true DLT rate in the under-, targeted or over-dose range. Furthermore, the average, minimum and maximum number of patients per trial and the average number of DLTs per trial are reported. Results are shown in Table 10.6: 3.

Table 10.6: 3

Simulated operating characteristics

Scenario	% of trials declaring an MTD with true DLT rate in				# Patients	# DLT
	underdose	target dose	overdose	STOPPED	Mean (Min-Max)	Mean (Min- Max)
1	22.7	61.6	0.2	15.5	17.05 (3 – 34)	2.896 (1 – 10)
2	9.5	52.0	14.8	23.7	15.38 (3 – 30)	3.642 (1 – 10)
3	26.2	73.8	0	0	19.77 (16 – 36)	2.236 (1 – 6)
4	5.5	79.2	5.7	9.6	17.78 (3 – 35)	3.664 (1 – 10)
5	14.4	85.4	0.2	0	19.60 (15 – 40)	3.303 (1- 8)

In scenario 1, which reflects the case that the true dose-toxicity is aligned with prior medians, 61.6% of the simulated trials declared a dose as MTD with true DLT rate in the targeted dose range. Note that 15.5% of the simulated trials stop because of high toxicity. This is mostly due to the cases that 1 DLT is observed out of 3 patients at the starting dose 40mg. In reality, this situation would rarely happen as the safety profile of starting dose is expected to be good. In addition, dose escalation could still happen after the discussion within DSB.

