4. CHANGES IN THE PLANNED ANALYSIS OF THE STUDY

5. ENDPOINT(S)

5.1 PRIMARY ENDPOINT(S)

The objective of this study is to determine the safety and tolerability of BI 836880. The primary endpoint is the determination of the maximum tolerated dose (MTD) of BI 836880 based on the number of patients with dose-limiting toxicities (DLTs) during the first treatment cycle. The DLT is defined in section 5.3.1 of the CTP.

The MTD is defined as the highest dose with less than 25% risk of the true DLT probability being above 33%, and may be considered reached if the probability that the true DLT rate is in target interval (16%-33%) is sufficiently large during the MTD evaluation period.

The DLT evaluation period is defined as the time within 3 weeks after first administration of study treatment. The evaluation period will be extended to two more weeks if treatment is delayed due to a drug related AE, For further details, please see CTP section 5.3.1.

Patients, who have not completed first cycle of treatment for other reason than DLT, will be replaced. Patients who were replaced during the MTD evaluation period will not be considered for MTD determination. Those patients that have completed the MTD evaluation period without having been replaced will be referred to as patients evaluable for MTD.

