7.4 PRIMARY ENDPOINT(S)

The primary endpoint is to assess the MTD based on the number of patients presenting DLTs during the MTD evaluation period. The primary analysis is for the determination of the MTD. The purpose of this analysis is to summarize and document the data that led to the selection of the MTD. Therefore, an overall summary of DLTs (see CTP section 5.3.1 for the definition of DLTs) which occurred during the MTD evaluation period will be provided for each dose cohort from the dose finding cohort treated set. Patients, if any, who did not complete the MTD evaluation period for reasons other than DLT will be excluded from the analysis of the primary endpoint.

A summary of the number of patients with DLTs overall in any course will be also given by initial treatment and displayed in a similar format to the summary of DLTs occurring in the MTD evaluation period.

The analysis of the MTD is based on a Bayesian logistic regression model (BLRM) guided by the escalation with overdose control principle. The MTD is defined as the highest dose for a given schedule that is expected to cause less than 25% risk of the true DLT rate being above or equal to 33% during the MTD evaluation period. Estimation of the MTD during the dose escalation phase of the study will be based upon the estimation of the posterior probability of the incidence of DLT in toxicity categories during the MTD evaluation period for all evaluable patients. The model to be used is specified in CTP section 7.

The posterior probabilities that the toxicity rates of each dose level fall into the categories specified in CTP section 7 will be displayed.

[figure not shown]

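### Protocol Section 7.1 gives the model's reference dose as 720 mg, but the printed prior means and the prior and posterior tables fit 1250 mg

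*Protocol*

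**What the plan says.** Protocol Section 7.1 models the first-cycle DLT probability as logit p(d) = log(alpha) + beta·log(d/d*). It sets d* to 720 mg, which "is the reference dose, allowing for the interpretation of" alpha as the DLT odds at d*. Three prior components are then derived from assumed median DLT rates at 40 and 720 mg:

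- Component 1 (weight 0.90): 0.1% at 40 mg, and "the median DLT rate at the anticipated MTD of 720mg would equal 20" per cent. Printed means for (log alpha, log beta): (-0.333, 0.647).
- Component 2 (weight 0.05): 10% and 50%. Printed means: (0.419, -0.274).
- Component 3 (weight 0.05): 0.1% and 2%. Printed means: (-3.316, 0.042).

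Table 7.1:2 shows "the prior probabilities of DLT at different doses, as well as the corresponding probability of under-, targeted and overdosing". Table 10.6:1 does the same for posterior data: "For each scenario, the probability of overdose for the current dose, as well as the next potential dose" are tabulated.

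The SAP builds the primary endpoint on this model. SAP 5.1: "The MTD is defined as the highest dose with less than 25% risk of the true DLT probability being above 33" per cent. SAP 7.4: "The model to be used is specified in CTP section 7". Neither document names 1250 mg as the reference dose.

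**The concern.** Component 2 shows the problem without software. A median DLT rate of 50% at d* forces log(alpha) = 0, yet 0.419 is printed. Read at d* = 720 mg, the three printed means imply DLT rates at 720 mg of 41.8%, 60.3% and 3.5%, not the stated 20%, 50% and 2%.

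The model supplies the overdose probabilities behind escalation and behind the SAP's definition of the MTD. If the stated constant does not belong to the stated prior, an analyst who codes Section 7.1 as written will not recover the protocol's tables, and some doses will fall on the other side of the 0.25 limit.

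**Working it through.** **1. Prior means from the anchors.** The slope is beta = [logit p(720) − logit p(40)] / ln(720/40), and log(alpha) = logit p(720) + beta·ln(d*/720). For component 1, beta = (−1.386 + 6.907)/2.890 = 1.910, so log(beta) = 0.647 as printed. At d* = 720, log(alpha) = −1.386. At d* = 1250 it is −1.386 + 1.910 × 0.5516 = −0.333. The last column solves for d* = 720·exp[(printed mean − logit p(720))/beta].

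| Component | beta | log(alpha), d* = 720 | log(alpha), d* = 1250 | Printed | Implied d* (mg) |
|---|---|---|---|---|---|
| 1 | 1.910 | −1.386 | −0.333 | −0.333 | 1249.8 |
| 2 | 0.760 | 0.000 | 0.419 | 0.419 | 1249.4 |
| 3 | 1.043 | −3.892 | −3.316 | −3.316 | 1250.5 |

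The log(beta) means do not depend on d*, and all three reproduce.

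**2. Table 7.1:2.** The printed three-component prior was pushed through the model by numerical integration. Prior P(overdose), meaning P(DLT rate ≥ 0.33):

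| Dose (mg) | Printed | d* = 1250 | d* = 720 |
|---|---|---|---|
| 40 | 0.074 | 0.072 | 0.090 |
| 120 | 0.116 | 0.115 | 0.150 |
| 360 | 0.205 | 0.205 | 0.300 |
| 720 | 0.332 | 0.335 | 0.568 |
| 1250 | 0.566 | 0.568 | 0.763 |

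With d* = 1250, every interval probability in the table agrees within 0.003. At d = d* the DLT rate depends on alpha alone, so the row for d* is fixed by the alpha means. That row comes out as 0.267/0.165/0.568. The protocol prints it (0.269/0.164/0.566) against 1250 mg, not 720 mg.

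**3. Table 10.6:1.** Posterior P(overdose) from the binomial likelihood of each scenario's data. The last column replaces the printed means by those the anchors give at d* = 720.

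| Scenario, dose (mg) | Printed | d* = 1250 | d* = 720, printed means | d* = 720, re-derived means |
|---|---|---|---|---|
| 1, 120 | 0.044 | 0.044 | 0.063 | 0.034 |
| 2, 40 | 0.278 | 0.276 | 0.287 | 0.229 |
| 3, 360 | 0.081 | 0.078 | 0.146 | 0.077 |
| 4, 120 | 0.194 | 0.189 | 0.210 | 0.157 |
| 5, 120 | 0.575 | 0.565 | 0.593 | 0.522 |
| 5, 40 | 0.236 | 0.232 | 0.213 | 0.198 |
| 6, 720 | 0.025 | 0.024 | 0.074 | 0.041 |
| 7, 720 | 0.224 | 0.224 | 0.384 | 0.287 |

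With d* = 1250, every cell of the table agrees within 0.013. Neither version with d* = 720 reproduces it. The re-derived means put scenarios 2 and 7 on the opposite side of 0.25 from the printed values, so keeping 720 and correcting the means does not rescue the text.

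**4. Effect on decisions (printed means, limit 0.25).** Except for scenarios 1–5, the data start with 0/2, 0/2 and 0/3 DLTs at 40, 120 and 360 mg.

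| Further data | Dose judged (mg) | d* = 720 | d* = 1250 | Same decision? |
|---|---|---|---|---|
| none | 720 | 0.343 | 0.114 | no |
| 0/3 at 720 (scenario 6) | 1000 | 0.295 | 0.126 | no |
| 1/3 at 720 (scenario 7) | 720 | 0.384 | 0.224 | no |
| 1/6 at 720 | 720 | 0.140 | 0.075 | yes, both pass |
| 2/6 at 720 | 720 | 0.407 | 0.278 | yes, both fail |
| 2/7 at 720 | 720 | 0.317 | 0.210 | no |
| scenarios 1–5 | as tabulated | – | – | yes |

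In scenario 7 the highest listed dose meeting the SAP 5.1 criterion is 360 mg (0.021) with d* = 720 and 720 mg (0.224) with d* = 1250, leaving aside the six-patient minimum.

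**The case against.** The inconsistency itself is hard to dispute. The case on the other side is about its weight.

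- **Effect on a declared MTD is narrow.** Section 7.1 requires at least six patients at the MTD, and the three main changes have zero or three at the dose judged. This stands. The 2/7 case crosses the limit with seven patients at 720 mg. Even there the trial has only 14 patients and a target-interval probability of about 0.45, so neither stopping condition (above 50%, or 18 patients) would yet be met.
- **Not every printed row discriminates.** Scenarios 2 and 4 separate the two values only weakly. This stands; the evidence rests on the prior means, Table 7.1:2 and scenarios 1, 3, 6 and 7. The high-toxicity row of Table 10.6:2 follows from the component 2 anchors at any d*. It helps only in that exp(0.419) = 1.52 is the odds of the 60.3% listed at 1250 mg, which repeats the argument from the means.
- **Only one of the three main changes is a printed row.** This is true: scenario 7 is printed, 1000 mg appears in no model table, and the move to 720 mg after three clean cohorts is only implied by scenarios 6 and 7.
- **Little practical harm.** With the printed means the changes found bar doses and do not release them. The reference in Protocol 6.2.2 to two ongoing patients suggests that escalation is over. Protocol 7.3.1 also lets other models supplement or replace this one. All fair, but the model in Section 7 is still the only written specification that SAP 7.4 points to for the primary analysis.

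**Conclusion.** The point holds. The anchors, the printed prior means and both tables agree with one another at d* = 1250 mg and disagree with the stated 720 mg. At 720 mg the prior P(overdose) is 0.568 by the text against 0.332 printed, and the scenario 7 value is 0.384 against 0.224.

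The demonstrated consequence is that the primary analysis cannot be reproduced from its written specification, with some overdose decisions reversed for anyone who follows it literally. The documents do not show which value any program used; the tables suggest that the design code used 1250. The calculations take the printed weights, means, standard deviations and zero correlations as given. The remaining gaps of up to 0.013 under d* = 1250 are assumed to be simulation error in the sponsor's figures. A wrong constant in the primary model must be corrected, even though the likely effect on a declared MTD is small.

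**What to change.** 1. Have the trial statistician confirm which d* was used in the design simulations, the runs for the Data Safety Board and the final-analysis code.
2. Reconcile Section 7.1 with its own means and tables: state d* = 1250 mg and read alpha as the odds of a DLT at 1250 mg. The 20%, 50% and 2% rates at 720 mg stay as derivation anchors.
3. State the same d* in SAP 7.4.
4. Re-run any model run that combined 720 with the printed means. If the check instead finds code using 720 with means re-derived for it, the printed means and both tables would have to be restated.

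The cost is a code check, one constant and one phrase in the protocol, and one line in the SAP. The sample size does not change.

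### Protocol 7.1 states a 20% median DLT rate at 720 mg, but its own prior table gives 14.8%, and the stated reference dose does not match the printed prior means

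*Protocol*

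**What the plan says.** Protocol section 7.1 defines a two-parameter logistic model with a stated reference dose d\* of 720 mg, "allowing for the interpretation of α as the odds of a DLT at dose d"\*. The prior is a mixture of three bivariate normal components for (log α, log β):

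- Component 1 (weight 0.9) assumes that "the median DLT rate at the starting dose of 40mg would equal 0.1" per cent and that "the median DLT rate at the anticipated MTD of 720mg would equal 20" per cent. Its means are given as (−0.333, 0.647), with SDs 2 and 1.
- Component 2 (weight 0.05) assumes 10% at 40 mg and 50% at 720 mg. Its means are (0.419, −0.274), with SDs 2 and 1.
- Component 3 (weight 0.05) assumes 0.1% and 2%. Its means are (−3.316, 0.042), with SDs 5 and 0.01.

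All correlations are 0. At 720 mg, Table 7.1:2 gives the mixture a median of 0.148, with probability 0.515 below 0.16 and 0.332 at or above 0.33. The text says that "the prior medians of the DLT probabilities are in-line with the prior medians derived from the weakly informative prior". In Table 10.6:1, scenario 7 (1 DLT in 3 patients at 720 mg after none at lower doses) has an overdose probability of 0.224 at 720 mg, and the next dose shown is 720 mg. The limit is 0.25 (footnote to Table 7.1:2; SAP section 7.4). SAP section 7.4 takes the model from the protocol without restating it.

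**The concern.** Section 7.1 gives 20% and 14.8% for what reads as the same quantity, the prior median DLT rate at the anticipated MTD. The first lies inside the target interval and the second below it.

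The prior drives overdose control in a first-in-human trial, so its description should match the prior in use. The stated reference dose also fails to reproduce the tables. A statistician who coded the model from the text would therefore get a different prior and could reach different escalation decisions.

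**Working it through.** **Step 1. Where the printed means come from.** Evaluate the curve at the parameter medians and solve for two stated rates:

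β = [logit p(720) − logit p(40)] / log(720/40), and log α = logit p(720) − β log(720/d\*).

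- Component 1: β = (−1.386 + 6.907)/2.890 = 1.910, so log β = 0.647, as printed. With d\* = 720 mg, log α would be −1.386, but −0.333 is printed. Solving back, log(d\*/720) = (−0.333 + 1.386)/1.910 = 0.551, so d\* is about 1250 mg.
- Component 2: β = 2.197/2.890 = 0.760, so log β = −0.274, as printed. Then log(d\*/720) = 0.419/0.760 = 0.551, again about 1250 mg.
- Component 3: β = (−3.892 + 6.907)/2.890 = 1.043, so log β = 0.042, as printed. Then log(d\*/720) = (−3.316 + 3.892)/1.043 = 0.552, again about 1250 mg.

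With d\* = 720 mg, the same assumptions give log α means of −1.386, 0.000 and −3.892.

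**Step 2. Reproducing the plan's figures.** The printed mixture was integrated numerically, with binomial likelihoods for scenario 7.

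| Quantity at 720 mg | Printed | d\* = 1250 mg | d\* = 720 mg (stated) |
|---|---|---|---|
| Prior median, mixture | 0.148 | 0.150 | 0.413 |
| Prior P(overdose) | 0.332 | 0.335 | 0.568 |
| Scenario 7 P(overdose) | 0.224 | 0.224 | 0.385 |

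The tables match 1250 mg, allowing for simulation error, and do not match 720 mg.

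**Step 3. Why 20% becomes about 15%.** With d\* = 1250 mg, component 1 at its parameter medians gives logit p(720) = −0.333 + 1.910 × log(720/1250) = −0.333 − 1.053 = −1.386, which is 20.0%. But β is lognormal with SD 1 on the log scale, and log(720/1250) is negative. The right-skewed slope pulls the distribution of p(720) down, and its marginal median is 14.6%. For component 2 the marginal medians are about 6.6% at 40 mg and 44.5% at 720 mg, against the stated 10% and 50%.

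If d\* is 720 mg, the slope term is zero at 720 mg and the median there is expit of the log α mean. The printed −0.333 gives 41.8%; the re-derived −1.386 gives exactly 20%.

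**Step 4. The mixture against component 1 (d\* = 1250 mg).**

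| Median at | 40 mg | 120 mg | 360 mg | 720 mg | 1250 mg |
|---|---|---|---|---|---|
| Component 1, recomputed | 0.0008 | 0.0056 | 0.040 | 0.146 | 0.418 |
| Mixture, Table 7.1:2 | 0.001 | 0.006 | 0.043 | 0.148 | 0.410 |

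**Step 5. Scenario 7 if the median at 720 mg really were about 20%.**

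| Rebuild | Median at 40 mg | Scenario 7 P(overdose) |
|---|---|---|
| All means re-derived, d\* = 720 mg | about 0.1% | 0.28–0.29 |
| d\* = 1250 mg, component 1 solved so that the mixture has both medians | 0.1% | 0.261 |
| d\* = 1250 mg, slope SD close to 0 | about 0.1% | 0.259 |
| d\* = 1250 mg, component 1 alone solved for both medians | about 0.1% | 0.255 |
| d\* = 1250 mg, intercept shift only | 0.14% | 0.252–0.253 |
| d\* = 1250 mg, slope change only | about 0.5% | 0.218 |

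**The case against.** Five points can be made on the other side.

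1. **A reader might infer that the stated parameters give 14.8%.** They do not. The stated parameters include d\* = 720 mg, which gives about 42% for component 1. The 14.8% needs a reference dose of 1250 mg, which section 7.1 never gives as d\*. This stands.
2. **A reader might treat the 20% against 14.8% gap as a second error, independent of the reference dose.** At 720 mg it is not. Re-deriving the means at the stated d\* gives exactly 20% for component 1 and 50% for component 2. What would remain is at 40 mg, where the component 2 median is about 6.5% and not 10%. This stands, and it is why d\* must be settled first.
3. **A reader might call the in-line sentence false.** It can fairly be read as comparing the mixture with component 1, and step 4 shows that those medians agree. It misleads only if taken to refer to the 20% assumption.
4. **A reader might say that a true 20% median would reverse the scenario 7 decision.** Step 5 runs from 0.22 to 0.29, and several rebuilds clear 0.25 by 0.01 or less. The slope-only case, however, gives up the stated 0.1% at 40 mg.
5. **A reader might say that the prior's caution is concealed.** Table 7.1:2 openly prints the tabulated prior. Before any data, 720 mg exceeds the 0.25 limit under both the printed prior (0.332) and the rebuilds (about 0.38–0.39), so its initial status does not change.

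These points narrow the concern. They do not remove the contradiction between the text, the stated d\* and the table.

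**Conclusion.** The specification is wrong as written. The stated 20% median at 720 mg is contradicted by the protocol's own 14.8%, and the printed means give 20% as a marginal median under neither reference dose: about 15% with 1250 mg, about 42% with 720 mg.

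The 20% is itself a correct value of the component 1 curve at its parameter medians with d\* = 1250 mg. It is simply not the prior median that Table 7.1:2 reports.

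That the tables used 1250 mg is an inference. It rests on all three mean vectors solving back to that value and on the tables reproducing with it. The documents do not show which d\* the running model uses. Any effect on a dose decision is conditional: scenario 7 passes 0.25 in the rebuilds that keep about 0.1% at 40 mg, and not in the slope-only rebuild.

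**What to change.** First, confirm from the model code which d\* is used, and reconcile it across the model definition, the mean vectors, Table 7.1:2 and Tables 10.6:1–3. Restating 14.8% before this is settled could entrench an error.

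- **If the tabulated prior (d\* = 1250 mg) is in use:** correct d\* in section 7.1. Give the marginal medians as about 0.1% at 40 mg and 15% at 720 mg, and for component 2 about 6.6% and 44.5%. Say that 0.1%/20% and 10%/50% are values at the parameter medians, and that the in-line sentence compares the mixture with component 1. The cost is one paragraph.
- **If a true 20% median was intended:** re-derive the means and rerun Table 7.1:2 and Tables 10.6:1–3. For example, component 1 means of (−1.386, 0.647) with d\* = 720 mg give exactly 20% at 720 mg. The cost is a rerun of the scenarios and of the five sets of 1,000 simulated trials.

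In either case, SAP section 7.4 should state d\* explicitly, because it takes the model from the protocol. No dose or dosing rule is proposed here; the sections must be reconciled.
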